- For MDS, responses must last at least 4 weeks (i.e., confirmation required at 4 weeks) and hematologic improvements (HI) must last at least 8 weeks. For AML, no minimum duration of response required to qualify for a given response.
- The assessment frequency for CR should also be applied to patients in CRm and CRc. Please refer to Appendix 7 for definitions.
- d Stable Disease (SD) is defined as failure to achieve a partial response but not meeting criteria for progressive disease. SD lasting for a period of more than 8 weeks is considered clinical benefit
- Progressive disease (PD) in AML is defined as previously having demonstrated partial remission or stable disease. For those with 5% to 66% bone marrow blasts at nadir, a > 50% increase in bone marrow blast count percentage from the nadir and percentage is \geq 20%; and for patients with \geq 67% bone marrow blasts at nadir, a doubling of the nadir absolute peripheral blood blast count with a final absolute peripheral blood blast count > 10×10^9 /L

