8.2 Treatment and Study Discontinuation

8.2.1 Treatment Discontinuation

Study treatment discontinuation occurs when a patient is no longer receiving any study drug (FT-2102, azacitidine, or cytarabine, as applicable). Treatment discontinuation is not necessarily accompanied by discontinuation from the study, as discussed in Section 8.2.2.

A patient should be discontinued from study treatment if, in the opinion of the Investigator, doing so is medically necessary, or if it is the wish of the patient. Reasons for discontinuation from study treatment may include any of the following:

- Unacceptable AE or failure to tolerate study therapy
- Delay in dosing of > 28 days, without approval of Sponsor
- Treatment failure (i.e., progression or relapse) (see Section 4.3, Table 3 for definition)
- Hematopoietic stem cell transplant (HSCT)
- Withdrawal of consent (no further study participation)
- Patient decision to discontinue study treatment
- Discretion of the Investigator
- Major protocol violation
- Pregnancy
- Lost to follow-up
- Death
- Termination of the study by Sponsor

All AEs leading to the discontinuation of study drug will be followed for 28 days after administration of last dose of study drug or until resolution or stabilization as documented by physical examination or appropriate laboratory results.

All patients who discontinue study treatment should undergo the End-of-Treatment assessments (see Section 6.1.23) and undergo Safety Follow-up (Section 6.1.24)/ enter Survival Follow-up (Section 6.1.26).

Patients who discontinue study treatment for reasons other than disease progression/relapse, including those who discontinue for HSCT, will continue to be followed for response duration until progression/relapse occurs (see Section 6.1.25).

Patients who discontinue treatment for HSCT should continue to be assessed for response as per the protocol-defined schedule.

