Appendix 7 Response Criteria for AML

Adapted from IWG Response Criteria (Cheson et al. 2003); see also Stein et al. 2017.

Response Category	Response criteria (no minimum duration required unless indicated)
Morphologic leukemia free state (MLFS)	 BM blasts < 5% (in aspirate with spicules and 200 nucleated cells) No blasts with Auer rods No extramedullary disease
Morphologic complete remission (CR)	Same as MLFS, and: $ \bullet ANC \geq 1000/\mu L $ $ \bullet Platelets \geq 100,000/\mu L $ $ \bullet Transfusion Independence $
Cytogenetic Complete Remission (CRc)	CR with no residual cytogenetic abnormalities ^a
Molecular Complete Remission (CRm)	CR with undetectable IDH1m minimal residual disease (MRD)
CR with incomplete hematologic recovery (CRi)	CR but with ANC $< 1000/\mu L$, or platelets $< 100,000/\mu L$
CR with partial hematologic recovery (CRh)	$<5\%$ BM blasts and partial recovery of peripheral blood counts (platelets >50 x $10^9/L$ and ANC >0.5 x $10^9/L)$
Partial remission (PR)	Reduction of BM blasts:
	• to a value between 5 % – 25%, if baseline was \geq 50%
	• by 50% to a value >5%, if baseline was between 5% - 49%
	Persistence of Auer rods, even if BM blasts ≤ 5%
	Hematologic values consistent with a CR:
	• ANC $\geq 1000/\mu L$ and
	• Platelets $\geq 100,000/\mu L$
Stable Disease (SD)	Failure to achieve at least a PR but not meeting criteria for progressive disease (PD). SD for a period of 8 weeks or more indicates clinical benefit

Response Category	Response criteria (no minimum duration required unless indicated)
Recurrence,	In patients who achieved CR, CRh, CRi, MLFS:
Morphologic Relapse	Reappearance of peripheral blasts, or
	• ≥ 5% BM blasts (if no peripheral blasts, may repeat BM assessment to distinguish relapse from BM regeneration)
	Development of extramedullary disease
Disease Progression	In patients with PR or SD:
	 For patients with 5% to 66% BM blasts at nadir, a >50% increase in BM blast count percentage from the nadir and percentage is ≥ 20%; and
	 For patients with ≥ 67% BM blasts at nadir, a doubling of the nadir absolute peripheral blood blast count with a final absolute peripheral blood blast count >10 x 10⁹/L
	New extramedullary disease

BM = bone marrow

^a Analysis by either conventional banded karyotyping or FISH is accepted

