Response assessments will be performed through evaluation of clinical findings and bone marrow/peripheral blood cell counts and morphology. Response criteria are derived from the International Working Group (IWG) response criteria for AML (Cheson et al. 2003) and MDS (Cheson et al. 2006) where applicable, and Stein et al. 2017, as outlined in the protocol section 4.3, Appendix 6 and Appendix 7.

Bone marrow for response assessment is required:

- at C2D1 if no peripheral blasts; otherwise, at C3D1, regardless of peripheral blast count;
- at least every 2 cycles (4 to 8 weeks) until morphologic complete remission (CR) is achieved, then up to every 3 cycles (for duration of response assessment) for 12 months after CR achievement, then up to every 6 cycles thereafter;
- when progressive disease is suspected;
- for Phase 2 Cohort 2 only: at C2D1, C4D1, C6D1 and every 6 cycles thereafter.

Response assessment requirements and frequency are the same for all subjects, including those that discontinue treatment due to hematopoietic stem cell transplant (HSCT).

In general, HSCT is not considered an event in time to event analyses. Patients who stop treatment with FT-2102 to have HSCT will continue to be monitored for duration of

response. HSCT is not considered an anti-leukemia therapy for purposes of analyses described herein.

In general, for the purposes of statistical analyses, relapse, progressive disease (PD), or disease progression will be treated interchangeably as being indicative of disease worsening.

AML Response: Following responses for AML will be evaluated by investigator based on the modified Cheson criteria (Cheson et al. 2003). Best overall response for each patient is selected based on the highest category achieved on study from the ordered list in the table below:

		Complete	Overall
Investigator Assessment of AML Response	CR/CRh	Response	Response
Molecular CR (CRm)		$\overline{\mathbf{v}}$	$\overline{\mathbf{v}}$
Cytogenetic CR (CRc)			
Complete Remission (CR)			
CR with Partial Hematologic Recovery (CRh)			
CR with incomplete recovery (CRi)			
Morphologic leukemia-free state (MLFS)			
Partial Remission (PR)			
Clinical Benefit			
Stable Disease			
Resistant Disease			
Relapse			
Progressive Disease (PD)			
Not Evaluable			
Not Done			

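### AML progression can be declared only after PR or SD, so first-assessment worsening reads as SD, and a best overall response of PD cannot arise from on-study AML assessments

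*Protocol*

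**What the plan says.** The progression footnote to Table 3 (Protocol Section 4.3, footnote e) opens: "Progressive disease (PD) in AML is defined as previously having demonstrated partial remission or stable disease". The blast thresholds come after that condition. Appendix 7 puts the same condition at the head of its AML progression criteria: "In patients with PR or SD".

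SD is a residual class. Footnote d reads: "Stable Disease (SD) is defined as failure to achieve a partial response but not meeting criteria for progressive disease". Appendix 7 says the same in substance, and AML responses need no minimum duration, so a single assessment can establish SD. Relapse is separate and applies "In patients who achieved CR, CRh, CRi, MLFS".

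SAP Section XI.A (AML Response) then sets the summary rule: "Best overall response for each patient is selected based on the highest category achieved on study from the ordered list". On that list SD ranks above Resistant Disease, Relapse and PD. Resistant Disease is not defined in Table 3 or Appendix 7.

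Protocol Section 8.2.1 sends the reader to Table 3 alone for one of its reasons for stopping treatment: "Treatment failure (i.e., progression or relapse) (see Section 4.3, Table 3 for definition". Footnote e does not mention extramedullary disease, whereas Appendix 7 lists "New extramedullary disease" as progression.

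**The concern.** At the first on-treatment marrow, a patient with active AML has normally shown neither PR nor SD on this study. If that patient has clearly worsened, the progression condition is not met, and the residual definition makes the result SD.

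SD is a named secondary endpoint in both phases, and SD of sufficient length is described as clinical benefit. A literal application would place some patients with primary progression in a favourable-sounding category, could move their EFS progression event to a later visit, and would leave one row of the planned best-response table empty by construction. An investigator who sees the gap may instead record PD or Resistant Disease, so the SD/PD split could depend on site habit.

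**Working it through.** The plan states no figure for this point, so the check follows the definitions.

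**1. One patient.** For illustration, take baseline blasts of 30% and 80% at C3D1. If baseline serves as the nadir, 30% lies in the 5% to 66% band, and the threshold is a rise of more than 50% (above 1.5 × 30% = 45%) to at least 20%. The value 80% passes both parts. The patient has no earlier PR or SD, so PD is not available. PR is not met either. The result is SD.

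**2. Best overall response.** Give each assessment one of four underlying states: remission, PR, no change, worse. Sequences of 1 to 4 assessments number 4 + 16 + 64 + 256 = 340. Classify each literally (PD only after PR or SD, relapse only after remission, otherwise SD) and take the best category.

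| Best overall response | Count, literal rule | Count, prior PR/SD condition dropped |
|---|---|---|
| Remission: Σ(4^L − 3^L) = 1 + 7 + 37 + 175 | 220 | 220 |
| PR: Σ(3^L − 2^L) = 1 + 5 + 19 + 65 | 90 | 90 |
| SD | 30 | 26 |
| PD | 0 | 4 |

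The last two rows share Σ2^L = 2 + 4 + 8 + 16 = 30 sequences. The 4 that change are those in which every assessment shows worsening, one for each length. These are counts of logical cases, not expected patient frequencies.

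**3. Who is outside the problem.**
- MDS: Appendix 8 sets progression by blast bands with no prior PR or SD, and its SD requires more than 8 weeks without progression.
- Cohort 2: patients enter in CR/CRi, so worsening is relapse.
- Patients with a PR or SD before enrolment or in an earlier cohort: the text does not limit the condition to this study. If that history counts, first-assessment worsening is PD. This matters most for rollovers into Cohorts 3 and 6.

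**4. EFS date.** SAP Section XI.A also counts treatment failure (best response below CRi), dated at the last response assessment on study.
- If the worsening visit is the last assessment, treatment failure carries that visit's date, the same date a PD call would give.
- If a further assessment follows, the literal rule can place progression no earlier than that assessment. The EFS date can then move later, unless death or new antileukemia therapy comes first.

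**5. Clinical benefit.** C2D1 is 28 days and C3D1 56 days (exactly 8 weeks) after C1D1. Footnote d asks for SD of more than 8 weeks; Appendix 7 asks for 8 weeks or more. If duration runs from first dose (an assumption), SD assigned at C3D1 meets the Appendix 7 wording but not footnote d.

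**6. Primary endpoint.** The Cohort 1 final rule of at least 36 responses in 173 has an exact one-sided tail probability of 0.0245 at a 15% rate, which matches the plan. Its power at 25% is 0.915 when the interim looks are ignored. Neither SD nor PD is a CR/CRh, so reclassification between them changes nothing here. ORR counts PR or better, and duration of response starts from such a response, so both are also unchanged.

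**The case against.** The strongest reply is that Section 4.3 offers these criteria as a guide and that the SAP tabulates the investigator's recorded category. No passage derives SD or PD from blast values. An investigator facing an obvious rise may well record PD or Resistant Disease. This stands: the documents do not show that patients with primary progression will in fact be counted as SD. It does not remove the defect, because the same section asks investigators for the protocol categories, and for this patient those categories, read literally, point to SD.

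Some stronger readings are tempting but not supported:
- **That no patient in the trial can have PD as best response.** MDS patients can, and Cohort 2 worsening is relapse.
- **That EFS progression is delayed by 168 days.** That is 6 cycles × 28 days, the routine AML marrow interval in the current Section 4.3. The SAP states marrow at least every 2 cycles until CR (2 × 28 = 56 days), and Section 4.3 requires a marrow whenever progression is suspected. Both figures are ceilings on a scheduled gap, not expected delays.
- **That 17 to 43 of 173 Cohort 1 patients move.** This needs an assumed primary progression rate of 10% to 25% and literal misclassification of every such patient. The documents give no such rate.
- **That the clinical-benefit count is inflated.** SD at C2D1 or C3D1 alone does not satisfy footnote d.

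On extramedullary disease, Section 4.3 points to Table 3 and the appendices together, so Appendix 7 may supply the missing item. Section 8.2.1, however, cites Table 3 alone.

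**Conclusion.** The defect holds for AML patients with active disease at entry and no earlier PR or SD. As written, worsening at their first on-treatment assessment is SD, and PD as best overall response cannot arise from on-study assessments, although the SAP carries that category. This is a stated rule that gives the wrong class, not a missing detail.

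The reach is limited to the AML SD count, the best-response table and, when a further assessment follows the worsening visit, the EFS date. The primary CR/CRh analysis is untouched, as are ORR and duration of response. The number of patients affected cannot be obtained from the documents.

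The conclusion assumes that the criteria are applied literally and that the earlier PR or SD must occur on study. If responses before enrolment count, fewer patients are affected. The correction is worth making because it is cheap, but it does not threaten the main result.

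**What to change.** **In the SAP, for analysis only:**
- State that worsening at the first assessment without prior PR or SD is not counted as SD in the best-response table and is an EFS event at that assessment.
- Name the reference value used to judge worsening, and say whether a PR or SD before enrolment or in an earlier cohort counts.
- Map Resistant Disease to a protocol category or remove it.
- Report a supportive re-derivation of SD/PD and EFS dates from recorded blast values alongside the investigator's assessment, not in place of it.

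**In the protocol:** the sponsor must reconcile Table 3, Appendix 7 and Section 8.2.1 on three matters: the prior PR/SD condition, new extramedullary disease, and the two versions of the 8-week limit. Table 3 also governs stopping of treatment, so this review does not propose the clinical progression or stopping rule.

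**Cost:** wording changes and programming on marrow and blood blast data already collected. The reported SD rate may become less favourable and EFS slightly shorter.

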4.4 Eligibility Criteria

4.4.1 Inclusion Criteria

To be considered eligible to participate in this study, a patient must meet ALL inclusion criteria listed below:

- 1. Pathologically proven AML (except acute promyelocytic leukemia with the t(15;17) translocation) or intermediate risk, high risk or very high risk MDS as defined by the World Health Organization (WHO) criteria or Revised International Prognostic Scoring System (IPSS-R) harboring IDH1-R132 mutations, and one of the following based on enrollment stage or treatment cohort:
 - a. Single Agent Phase 1 Cohorts including Dose-Escalation/ Dose-Expansion: AML/MDS either R/R to standard therapy, or for whom standard treatments are contraindicated
 - b. Combination (FT-2102 + azacitidine) Phase 1 Dose-Escalation/ Dose-Expansion (patients must meet one of the following):
 - i. Patients with AML that is either R/R to standard therapy, or for whom standard treatments are contraindicated
 - ii. Patients with MDS that is either R/R to standard therapy, or are treatmentnaïve, who are eligible for azacitidine therapy
 - c. Combination (FT-2102 + cytarabine) Phase 1 Dose-Escalation/Dose-Expansion Cohort: Patients ≥ 60 years with treatment-naïve AML for whom standard treatments are contraindicated
 - d. Phase 2 Cohort 1 (Single Agent) only: AML R/R to standard therapy
 - e. **Phase 2 Cohort 2 (Single Agent) only:** AML in morphologic CR/CRi after prior therapy (+/- HSCT) with residual IDH1-R132 mutation (≥ 0.01%) detected in the bone marrow
 - f. **Phase 2 Cohort 3 (Single Agent) only:** R/R AML/MDS that have been previously treated with FT-2102 **AND** for whom standard treatments are contraindicated
 - g. **Phase 2 Cohort 4 (FT-2102 + Azacitidine) only:** Patients < 60 years old with R/R AML/MDS with no prior hypomethylating agent therapy **AND** no prior IDH1 inhibitor therapy
 - h. **Phase 2 Cohort 5 (FT-2102 + Azacitidine) only:** R/R AML/MDS that have inadequately responded to or have progressed on prior treatment with a hypomethylating agent

- i. Phase 2 Cohort 6 (FT-2102 + Azacitidine) only: R/R AML/MDS that have been previously treated with single agent FT-2102 as their last therapy prior to study enrollment
- j. **Phase 2 Cohort 7 (Single Agent) only:** Treatment naïve AML patients for whom standard treatments are contraindicated
- k. **Phase 2 Cohort 8 (FT-2102 + Azacitidine) only:** Treatment naïve AML patients who are candidates for azacitidine as a first line treatment
 - Note for Phase 2 Cohort 7 and Phase 2 Cohort 8: Treatment naïve is defined as no prior treatment for AML. Patients may have received a prior treatment for another hematologic malignancy.
- 2. Patients must have documented IDH1-R132 gene-mutated disease as evaluated by the site
- 3. Patients \geq 18 years old
- 4. Eastern Cooperative Oncology Group (ECOG) performance status of 0 to 2 (see Appendix 3)
- 5. Signed informed consent prior to beginning study and undergoing procedures
- 6. No prior solid organ allograft
- 7. Acceptable liver function:
 - a. Bilirubin ≤ 2 times upper limit of normal (ULN) (≤ 3 times ULN in patients with Gilbert Syndrome)
 - b. Aspartate transaminase (AST, also referred to as SGOT), alanine transaminase (ALT, also referred to as SGPT) and alkaline phosphatase (ALP) \leq 3 times ULN
- 8. Acceptable renal function:
 - a. Serum creatinine ≤ 1.5 times ULN or calculated creatinine clearance ≥ 50 mL/min (Cockcroft and Gault 1976)
- 9. Recovery from the non-hematologic toxic effects of prior treatment to Grade ≤ 1, or baseline value according to NCI CTCAE classification (excluding infertility, alopecia, or Grade 1 neuropathy)
- 10. Baseline OTcF < 450 msec (average of the OTcF values of screening triplicate ECGs)

Note: This criterion does not apply to patients with a bundle branch block (BBB); for patients with BBB, a cardiology consult is recommended to ensure that QTcF is not prolonged.

- 11. Negative serum pregnancy test if female of childbearing potential
- 12. For fertile men and women, agreement to use highly effective contraceptive methods for the duration of study participation and 90 days after the last dose of study medication (Section 5.6.1)
- 13. Agreement for male patients not to donate sperm and for female patients of childbearing potential not to donate ova during the study and for 90 days after the final dose of study drug (see Section 5.6.2)
- 14. **Phase 2 Cohorts 1 8 (SA and combination) only:** Pre-treatment peripheral blood and bone marrow aspirate available for retrospective central confirmation of IDH1-R132 mutation is required.

Note: Central confirmation of IDH1-R132 mutation is not required for study enrollment.

4.4.2 Exclusion Criteria

To be eligible for entry into the study, the patient must NOT meet any of the exclusion criteria listed below:

- 1. Phase 1 Single Agent Dose-escalation/Dose-expansion Cohorts and Phase 2
 Cohorts 1, 4, 5, 7 and 8 only: Patients who have been treated with an IDH1 targeted therapy are excluded
- 2. **Phase 2 Single Agent Cohorts 1-3 and 7 only:** Patients with IDH2 mutation detection at baseline or history of IDH2m inhibitor treatment are excluded
- 3. History of prior malignancy unless disease-free for ≥ 12 months or considered surgically cured; patients with nonmelanoma skin cancers or with carcinomas in situ are eligible regardless of the time from diagnosis (including concomitant diagnoses)
- 4. Patients with symptomatic central nervous system (CNS) metastases or other tumor location (such as spinal cord compression, other compressive mass, uncontrolled painful lesion, bone fracture, etc.) necessitating an urgent therapeutic intervention, palliative care, surgery or radiation therapy
- 5. Patients with previous allogeneic HSCT, if they meet any of the following criteria: < 100 days from time of HSCT; active acute or chronic graft vs. host disease (GvHD); or receiving immunosuppressive therapy as treatment or prophylaxis against

GvHD

Note: Doses < 20 mg methylprednisolone (or its equivalent) daily are not an exclusion criterion.

- 6. Treatment with radiation therapy, major surgery (requiring general anesthesia) within one month prior to study drug dosing
- 7. Treatment with chemotherapy or small molecule anticancer therapeutic within five half-lives of the agent or within 21 days if the half-life is unknown. Patients reenrolling in Cohort 6 after relapse/progression on Cohort 1 are exempt from this washout requirement (i.e. can continue FT-2102 treatment until re-enrollment)
- 8. Treatment with an anticancer therapeutic antibody less than four weeks before first dose of study drug
- 9. Treatment with other experimental therapies or participation in another clinical trial within a period of time that is less than the cycle length or within 21 days prior to starting study drug, whichever is shorter
- 10. Patients unable to swallow oral medications, or patients with gastrointestinal conditions (e.g., malabsorption, resection, etc.) deemed by the Investigator to jeopardize intestinal absorption
- 11. Congestive heart failure (New York Heart Association Class III or IV) or unstable angina pectoris; previous history of myocardial infarction within one year prior to study entry, uncontrolled hypertension, or uncontrolled arrhythmias (see Appendix 5)
- 12. Patients with a family history of QT prolongation
- 13. Concomitant medication(s) known to cause Torsades de Pointes (TdP) initiated less than the duration required to reach steady-state plasma concentration (approximately five half-lives)before first dose of study drug (see Appendix 6) (medications used as needed [PRN] (e.g. Zofran) are exempt)
- 14. Concurrent treatment with chronic corticosteroids except if chronic treatment with < 20 mg of methylprednisolone daily or equivalent (pulse steroids for treatment or prophylaxis are allowed [e.g., for transfusion or medication reactions])
- 15. Known HIV positivity
- 16. Active, uncontrolled bacterial, viral, or fungal infections, requiring systemic therapy (prophylactic systemic antimicrobials permitted)

- 17. Uncontrolled disease-related metabolic disorder (e.g., hypercalcemia)
- 18. Pregnant or nursing women or women of childbearing potential not using highly effective contraception; male patients not using highly effective contraception Note: Women of childbearing potential (see Section 5.6) and men must agree to use highly effective contraception (see Section 5.6.1) prior to study entry and for the duration of study participation and 90 days after.
 - Should a woman become pregnant or suspect she is pregnant while participating in this study, she should inform her treating physician immediately.
- 19. Serious nonmalignant disease (e.g., hydronephrosis, liver failure, or other conditions) that could compromise protocol objectives in the opinion of the Investigator and/or the Sponsor
- 20. Unwillingness or inability to comply with procedures either required in this protocol or considered standard of care
- 21. Medical, uncontrolled disease-related metabolic disorder, psychiatric, cognitive, or other conditions that may compromise the patient's ability to understand the patient information, give informed consent, comply with the study protocol, or complete the study
- 22. History of severe allergic reaction to azacitidine (if patient enrolling into azacitidine combination cohort) or low-dose cytarabine (if patient enrolling into cytarabine combination cohort)
- 23. Prisoners or patients who are involuntarily incarcerated or are compulsorily detained for treatment of either a psychiatric or physical (e.g. infectious disease) illness Note: Under certain specific circumstances, a person who has been imprisoned may be included or permitted to continue as a patient, if local regulations permit. Strict conditions apply and Forma's approval is required.

Note: Eligibility criteria waivers will not be granted.

